1. INTRODUCTION

1.1. Disease Background

Sickle cell disease (SCD) is a rare, devastating, and debilitating disease marked by the pathophysiologic features of hemolytic anemia, vaso-occlusion, and progressive end-organ damage, with a clinical course characterized by life-long disability and early death. In addition to unpredictable and recurrent episodes of severe pain, commonly referred to as painful crises, a systemic vasculopathy leads to chronic and progressive tissue injury across multiple organ systems. Multiple pathophysiologic mechanisms likely contribute to the systemic vasculopathy, including importantly, chronic hemolytic anemia (Rother, 2005).

The most devastating complication of pediatric SCD is the development of central nervous system events such as overt stroke or silent cerebral infarcts which can produce significant physical and neurocognitive deficits (Ohene-Frempong, 1998; DeBaun, 2016). Transcranial Doppler (TCD) ultrasonography to assess cerebral artery blood flow velocity in children with SCD has been shown to be a reliable predictor of stroke (Adams, 1992). Patients with "abnormal" TCD flow velocities (\geq 200 cm/sec) are at high risk of stroke, which can be mitigated by chronic red blood cell (RBC) transfusion or hydroxyurea (HU) (Adams, 1998; Adams, 2005; Ware, 2016). Because of these findings, practice guidelines recommend that all children with Sickle Cell Anemia (HbSS or HbS β^0 thal) should be screened annually with TCD according to methods employed in the STOP (Optimizing Primary Stroke Prevention in SCD) studies, beginning at age 2 and continuing until at least age 16 (NIH, 2014; Yawn, 2014).

Patients with "conditional" TCD flow velocities (\geq 170 to < 200 cm/sec) are at lower risk of stroke than patients with abnormal TCD flow velocities (risk for conditional is approximately 2% per year, for abnormal is approximately 9% per year, and for healthy children without SCD is < 0.1% per year), but still have significantly elevated stroke risk. Practice guidelines recommend that patients with conditional TCD flow velocities undergo more frequent screening and referral to specialist care for stroke prevention. Currently there is no standard-of-care therapy indicated to reduce stroke risk or prevent future need for transfusions in patients with conditional TCD flow velocities.

As current treatment options are limited, there remains a significant unmet medical need for novel therapies and for the early treatment of pediatric patients with SCD to mitigate the consequences of the disease (Steinberg, 2003). None of the currently-approved SCD therapies target the underlying mechanism of the disease to prevent the polymerization of sickle hemoglobin (HbS) and the sickling of RBCs which in turn underlies the serious and life-threatening clinical complications of SCD (Bunn, 1997).

1.2. Voxelotor

Voxelotor (formerly known as GBT440) is an orally administered small molecule that inhibits HbS polymerization by allosterically modifying hemoglobin-oxygen (Hb-O₂) affinity, and is approved in the United States (US) for use in patients with sickle cell disease (SCD) who are 12 years and older (Oxbryta[®] United States Prescription Information [USPI]). Marketing approval in other regions has been received or is being sought. For details on the global registration status, please refer to the current Investigator's Brochure (IB), which is the Single Reference Safety Document (SRSD) for this study.

Voxelotor was designed to bind to HbS with preferential partitioning into RBCs. It binds covalently and reversibly via Schiff base to the N-terminal value of the Hb α chain (ie, a single voxelotor molecule binding per HbS tetramer in a 1:1 stoichiometry) and allosterically (Eaton, 1999) increases sickle hemoglobin-oxygen (HbS-O₂) affinity (Oksenberg, 2016), stabilizing the oxyHb state and inhibiting polymerization (Oksenberg, 2016). The voxelotor binding site is distant from heme pockets and therefore it can increase oxygen (O₂) affinity without sterically blocking the release of O₂.

A primary and obligatory event in the molecular pathogenesis of SCD is the polymerization of deoxygenated HbS which results in RBC membrane damage, destruction, and resulting clinical consequences of hemolytic anemia and vaso-occlusion leading to chronic organ injury, debilitating symptoms, and early mortality. Because oxyhemoglobin (oxyHb) is a potent inhibitor of HbS polymerization, increasing the proportion of oxyHb in all RBCs with voxelotor can reduce HbS polymerization, decrease RBC membrane damage and destruction and has the potential to subsequently achieve long term disease modification. This principle is supported by the finding that in patients with sickle hereditary persistence of fetal hemoglobin, the dilution of HbS by 20% to 30% fetal hemoglobin (HbF) in all RBCs is sufficient to inhibit HbS polymerization, preventing RBC damage and SCD clinical sequelae. This suggests that pharmacologically maintaining approximately 20% to 30% of hemoglobin (Hb) in the nonpolymerizing oxygenated state in all RBCs may be an effective approach for the treatment of SCD. By addressing the multiple underlying mechanistic culprits of stroke in patients with SCD including low Hb, hemolysis and mechanistic culprits of stroke in patients with SCD including low Hb, hemolysis and polymerization (Adams, 2005; Kwiatkowski, 2010; Platt, 2008), voxelotor has the potential to constitute a disease modifying therapy and alleviate clinical manifestations of SCD (Perrine, 1972; Natta, 1974; Bethlenfalvay, 1975; Stamatoyannopoulos, 1975; Talbot, 1983; Akinsheye, 2011; Akinsheye, 2012).

In this study, the neurologic and the overall benefits and risks of long-term treatment (up to 96 weeks) with voxelotor in pediatric participants 2 to < 15 years of age will be investigated.

1.3. Summary of Relevant Nonclinical Data and Clinical Data

1.3.1. Nonclinical Data

Primary pharmacodynamics (PD) studies of voxelotor consisted of in vitro and in vivo studies to characterize (a) voxelotor binding and affinity for Hb, (b) the effect of voxelotor on HbS modification using purified Hb, washed RBCs, and whole blood, and (c) the efficacy of voxelotor in vivo in a mouse model of SCD. These in vitro assays of increasing complexity included measuring Hb-O₂ via hemoximetry, quantifying stabilization of the oxyhemoglobin state conformation, delaying HbS polymerization at low O₂ tension, preventing in vitro sickling induced by a low O₂ environment, decreasing viscosity and improving deformability of RBCs in blood from patients with SCD (Dufu, 2018). In addition, these studies show that voxelotor-modified Hb retains the Bohr Effect, which is the ability to offload O₂ from Hb in metabolically active (low pH) tissues.

Collectively, these studies demonstrate that voxelotor increases Hb-O₂ affinity with high specificity of binding to Hb, stabilizes the oxy or R-state conformation of Hb, prevents HbS polymerization and RBC sickling in vitro, and improves sickle blood viscosity and deformability in vitro. In addition, voxelotor increases HbS-O₂ affinity and RBC half-life, while decreasing ex vivo sickling and reticulocyte count in a SCD mouse model.

Additional information regarding nonclinical pharmacology (including safety pharmacology and metabolism) and toxicology is provided in the most current version of the voxelotor IB, provided separately.

1.3.2. Clinical Data

The Phase 3 double-blind, randomized, placebo-controlled study, Study GBT440-031, in which adults and pediatric participants (aged 12 to 17 years) received placebo, voxelotor 900 mg, or voxelotor 1500 mg is completed. In this study, voxelotor was shown to significantly increase Hb, improve anemia, and reduce clinical measures of hemolysis in adult and pediatric participants 12 years of age and older with SCD.

Information regarding the safety and tolerability, and efficacy of voxelotor is provided in Section 1.4 and detailed in the current version of the voxelotor IB.

1.4. Summary of the Known and Potential Risks and Benefits of Voxelotor

Clinical data to date have shown that treatment with voxelotor results in a dose-dependent increase in Hb within 2 weeks that is maintained through 24 weeks, and with an associated decrease in clinical measures of hemolysis (including indirect bilirubin, reticulocytes, and LDH), which correlates with drug exposure (Brown, 2018; Vichinsky, 2018). Durability of response is sustained through 72 weeks of treatment (Howard, 2021). By stabilizing HbS in the oxy-Hb state, voxelotor delays in vitro HbS polymerization and prevents RBC sickling in blood from patients with SCD (Oksenberg, 2016). By inhibiting HbS polymerization, voxelotor has been shown to improve RBCs deformability and reduce blood viscosity. Treatment with voxelotor has also led to significant reductions in sickle cell counts in the peripheral blood (Dufu, 2018), which support the potential for voxelotor to serve as a disease-modifying therapy for SCD.

Based on available data, voxelotor has been well tolerated over a range of tested doses up to and including 1500 mg daily in adult and pediatric clinical study participants with SCD (Studies GBT440-031, GBT440-001, and GBT440-007). There have been no concerning safety findings arising from review of data from the completed Phase 3 Study GBT440-031 and the ongoing Phase 2 pediatric study, GBT440-007.

Based on the safety data from the Phase 3 study in adult and adolescent participants with SCD, non-SCD-related treatment-emergent adverse events (TEAEs) were predominantly of low-grade severity and were transient. Identified risks include the adverse drug reactions (ADRs) of diarrhea, abdominal pain, nausea, rash, and drug hypersensitivity. As expected, SCD-related TEAEs were common, and the incidence of SCD-related TEAEs, including sickle cell anemia (SCA) with crisis, was similar for the voxelotor and placebo treatment groups. The profile of non-SCD-related and SCD-related TEAEs in adolescent participants was similar to the voxelotor treatment groups in the adult population.

Across all SCD studies, the overall incidence of TEAEs leading to study treatment discontinuation was low and the most commonly reported serious adverse events (SAEs) were predominantly assessed as not related to study treatment but to underlying SCD; predominantly SCA with crisis.

Overall, no clinical safety concerns consistent with inadequate tissue oxygenation were identified in the voxelotor clinical development program, including participants with SCD. Of particular note, maximal exercise testing in patients with SCD (Howard, 2019) and healthy volunteers exposed to hypoxic (12.5%) conditions have shown no detrimental effects of voxelotor on clinically relevant physiologic parameters that would indicate hypoxic tissue stress (eg, vital signs, cardiac output, lactate, exercise capacity, dyspnea and perceived exertion, mental status) (Stewart, 2018a, Stewart, 2018b, Hutchaleelaha, 2019).

The evidence generated by clinical studies and post-marketing experience suggests there is no increased risk of VOC after abrupt discontinuation of voxelotor.

Taken together, the safety outcomes and efficacy from clinical studies to date demonstrate an acceptable risk-benefit profile of voxelotor and support its continued development in pediatric participants with SCD. In Study GBT440-032, participants with conditional TCD flow velocities (≥ 170 to < 200 cm/sec) will be enrolled. Currently there are no standard-of-care therapies indicated to reduce stroke risk or prevent future need for transfusions in patients with conditional TCD flow velocities. Treatment with voxelotor may reduce the stroke risk in participants with conditional TCD flow velocity at baseline.

Additional information regarding clinical studies and safety is available in the most current version of the voxelotor IB.

1.5. Study Rationale

The purpose of Study GBT440-032 is to evaluate the effect of voxelotor on stroke reduction, as measured by TCD flow velocity in participants 2 to < 15 years of age with SCD who have conditional TCD flow velocity at baseline.

The primary endpoint of this study is change from baseline at 24 weeks in time averaged maximum of mean velocity (TAMMV) arterial cerebral blood flow as measured by TCD.

A reduction in stroke risk, using TCD flow velocity as an endpoint is based on the following:

- Anemia was the single most powerful predictor of stroke in a multivariate analysis in patients with SCD without prior history of stroke/transient ischemic attack (TIA) (RR: 1.85 per 1 g/dL decrease in Hb for stroke; p < 0.001) (Ohene-Frempong, 1998).
- TCD flow velocity is strongly associated with long-term stroke risk reduction after adjustment for other patient factors (Adams, 1992).
- An abnormal TCD flow velocity is an indication for primary stroke prophylaxis with chronic blood transfusion; conditional TCD flow velocity also confers elevated stroke risk (2% to 5% [Hankins, 2008]) and requires frequent monitoring (Adams, 1997; NHLBI, 2014; Zétola, 2012), and a 15 cm/s reduction in TCD flow velocity is clinically meaningful (Hankins, 2015).

1.6. Description of and Justification for the Route of Administration, Dosage, Dosage Regimen, and Treatment Period(s)

Voxelotor is available in an oral form and is intended for once daily administration. See below, and Section 3.1.1 and Section 5.1 for additional information regarding the dose to be used in this study.

1.6.1. Dose Rationale

The doses of voxelotor to be evaluated in this study are 1500 mg orally daily for participants \geq 12 years of age or a 1500-mg weight-based adult equivalent (see Table 1) for participants < 12 years of age. This dose of voxelotor is supported by: (1) absence of concerning exposure-related safety findings from the pivotal Phase 3 study GBT440-031 in adults and adolescents with SCD; (2) a statistically significant and clinically meaningful increase in Hb, and reductions in clinical measures of hemolysis observed with voxelotor 1500 mg, which were more robust than those observed with voxelotor 900 mg (Vichinsky, 2018); 3) the efficacy of the 1500-mg dose in adolescents is supported by similar improvements in Hb and hemolysis measures observed in the Phase 2a Study GBT440-007 (Brown, 2018); 4) exposure-response analyses using data from both Study GBT440-031 and Study GBT440-007 demonstrating dose-dependent treatment effects of voxelotor on Hb and hemolysis measures; 5) the majority of adult and adolescent participants receiving voxelotor 1500 mg in the GBT440-031 study achieved the intended therapeutic target of 20% to 30% mean % Hb occupancy.

Dosing for participants < 12 years of age will be weight based, as presented in Table 1 and Table 2, and is anticipated to provide exposures similar to adolescent participants receiving voxelotor 1500 mg. These doses are based on population pharmacokinetics (PPK) utilizing allometric scaling and are expected to provide exposures of voxelotor equivalent to exposures observed in adults (Study GBT440-031) and adolescents (Studies GBT440-007 and GBT440-031) (Washington, 2018).

Two dosage forms of voxelotor may be evaluated in this study for participants < 12 years of age; powder for oral suspension or dispersible tablet. To estimate appropriate doses of voxelotor powder for oral suspension to be evaluated in pediatric participants (2 years to < 12 years) with SCD, multiple doses of voxelotor were simulated by weight group (5 kg to < 10 kg, 10 kg to < 20 kg, and 20 kg to < 40 kg). The simulations were based on a voxelotor whole blood PPK model, including data from adults, adolescents, and children aged 6 to 11 years. The model used the same model structure (ie, 2-compartment model with first-order absorption) as the adult PPK model. The clearance (CL) and central volume (V_c) were scaled allometrically based on participant weights sampled from age-stratified normal distributions for children with homozygous SCD (Thomas, 2000).

A bioequivalence study in healthy volunteers (Study GBT-0119) showed that a single dose of the powder for oral suspension dosage form had an approximately 35% greater exposure than the same milligram dose of dispersible tablet. Therefore, for participants in this study receiving the dispersible tablet dosage form, the dose of the dispersible tablet will be increased by 35% relative to the powder for oral suspension dose to adjust for the difference in the dosage form (see Table 1 and Table 2).

It is intended that the powder for oral suspension dosage form will be used throughout the entire study. The dispersible tablet dosage form will only be used in this study if the supply of powder for oral suspension is insufficient to complete the study.

Table 1: Voxelotor Powder for Oral Suspension Weight-Based Doses for Participants Less than 12 Years of Age

Population	on 1500 mg-Equivalent Adult Dose	
10 to < 20 kg	600 mg	
20 to < 40 kg	900 mg	
≥40 kg ^a	1500 mg	

Note: All participants \geq 12 years of age will take voxelotor 1500 mg administered as tablets, regardless of their weight.

^a Voxelotor will be administered as 500 mg tablets.

Table 2: Voxelotor Dispersible Tablet Weight-Based Doses for Participants Less than 12 Years of Age

Population	1500 mg-Equivalent Adult Dose	
10 to < 20 kg	800 mg	
20 to < 40 kg	1200 mg	
≥ 40 kg ^a	1500 mg	

Note: All participants \geq 12 years of age will take voxelotor 1500 mg administered as tablets, regardless of their weight.

^a Voxelotor will be administered as 500 mg tablets.

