5.1.2. Dose Modification

Participants should adhere to their dose level assigned at Day 1.

For AEs that impact safety and tolerability, a trial of reducing or holding the dose may be used. All instances of study drug dose modification (dose reduction, interruption, or discontinuation) should be documented in the participants' medical record and recorded on the electronic case report form (eCRF). If the conditions/event leading to the dose modification have resolved, the original dose level should be resumed unless in the judgment of the Investigator this cannot be done safely. Dose reductions due to AEs are provided in Table 3 and Table 4 for participants < 12 years of age and Table 5 for participants ≥ 12 years of age.

Table 3: Weight-based Dose Reductions for Participants < 12 Years of Age Receiving Powder for Oral Suspension

Weight	Voxelotor 1500 mg Dose Equivalent	Dose Reduction 1 New Dose	Dose Reduction 2 New Dose
10 to < 20 kg	600 mg	400 mg	300 mg
20 to < 40 kg	900 mg	600 mg	400 mg
\geq 40 kg ^a	1500 mg	1000 mg	500 mg

^a Voxelotor will be administered as 500 mg tablets.

Table 4: Weight-based Dose Reductions for Participants < 12 Years of Age Receiving Dispersible Tablet

Weight	Voxelotor 1500 mg Dose Equivalent	Dose Reduction 1 New Dose	Dose Reduction 2 New Dose
10 to < 20 kg	800 mg	500 mg	300 mg
20 to < 40 kg	1200 mg	900 mg	300 mg
≥40 kg ^a	1500 mg	1000 mg	500 mg

^a Voxelotor will be administered as 500 mg tablets.

Table 5: Dose Reductions for Participants ≥ 12 Years of Age Receiving Voxelotor Tablets

Initial Dose	Dose Reduction 1 New Dose	Dose Reduction 2 New Dose
1500 mg ^a	1000 mg	500 mg

* Voxelotor will be administered as 500 mg tablets.

Guidelines for dose reduction, dose interruption, or permanent discontinuation of study drug for study drug-related AEs are provided in Table 6. If in the opinion of the Investigator, the AE resolves after a dose reduction, participants may resume study drug at the original dose The Medical Monitor should be notified of all dose modifications due to AEs within 5 days. The Medical Monitor may be consulted as needed.

Table 6:	Dose Modification Guidelines for Study Drug-Related Adverse Events
Table U.	Dust Mounication Outdemits for Study Drug-Actated Adverse Events

Dose Reduction		
Event	Recommended Action	

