Grade ≥ 2 (NCI grading scale) AE deemed considered related to study drug by the Investigator AND Precludes continued dosing at the current dose level due to safety concern or lack of tolerability (in the Investigator's judgment)	Study drug : May be reduced by one dose reduction. If, in the opinion of the Investigator, a Grade 2 AE has resolved to \leq Grade 1, participant may resume study drug at the original dose. If, in the opinion of the Investigator, the AE poses a significant safety concern such that a dose hold is considered, the Investigator should contact the Medical Monitor.	
ALT \geq 3 × ULN if ALT within normal limits at baseline OR > 3 × ULN AND a \geq 2-fold increase above baseline value if elevated ALT value at baseline in the absence of additional signs of	Study drug : Confirm by repeat testing within 48 to 72 hours, if possible, then repeat liver panel at least weekly until ALT level improves.	

compromised liver function such as elevated PT, PTT, INR, elevated conjugated bilirubin, jaundice, or hepatic pain	Additional actions: If ALT level continues to increase, reduce dose by one dose reduction and notify the Medical Monitor.
ALT \geq 5 × and < 8 × ULN (confirmed by repeat testing within 48 to 72 hours) in the absence of additional signs of compromised liver function such as elevated PT, PTT, elevated conjugated bilirubin, jaundice, or hepatic pain	Study drug : Reduce dose by one dose reduction. Additional actions : Repeat liver panel test within 48 to 72 hours if possible and then at least weekly until resolution to < 5 × ULN; if ALT does not improve within 2 weeks of dose reduction, the Medical Monitor should be notified. If ALT continues to increase within 1 week after a dose reduction, dose should be interrupted, and the Medical Monitor should be notified.
Dose Interruption (Hold)	
Event	Recommended Action

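### The second dose reduction for the dispersible tablet in Table 4 (300 mg in both weight bands below 40 kg) does not fit the exposure rationale in Section 1.6.1, most clearly at 20 to < 40 kg, and nothing explains it

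*Protocol*

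**What the plan says.** Protocol Section 1.6.1 (Dose Rationale) cites a single-dose study in healthy volunteers in which the powder for oral suspension "had an approximately 35% greater exposure than the same milligram dose of dispersible tablet". From this it concludes that "the dose of the dispersible tablet will be increased by 35% relative to the powder for oral suspension dose", and refers to Tables 1 and 2, which hold the full doses. The tablet is a fallback: "The dispersible tablet dosage form will only be used in this study if the supply of powder for oral suspension is insufficient".

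Section 5.1.2 (Dose Modification) gives the reduced doses for adverse events in three tables: "Table 3: Weight-based Dose Reductions for Participants < 12 Years of Age Receiving Powder for Oral Suspension", "Table 4: Weight-based Dose Reductions for Participants < 12 Years of Age Receiving Dispersible Tablet" and "Table 5: Dose Reductions for Participants ≥ 12 Years of Age Receiving Voxelotor Tablets". Each has two reduction steps. Table 6 then tells sites when to use them, for example "reduce dose by one dose reduction and notify the Medical Monitor", without distinguishing dosage forms. Reductions can be reversed: "If the conditions/event leading to the dose modification have resolved, the original dose level should be resumed", unless the investigator judges this unsafe.

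Section 5.3.1 gives the dispersible tablet strengths as 100 mg and 300 mg.

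**The concern.** Section 1.6.1 gives a reason for the tablet dose to be higher in milligrams than the powder dose: the tablet delivers less exposure per milligram. At the second reduction, Table 4 goes the other way. The tablet dose equals the powder dose in the lower band and is below it in the upper band. The two tablet bands also share one dose at that step, whereas Table 3 keeps the two powder bands apart at every step.

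Sites would take these printed doses when Table 6 calls for one dose reduction. If the 35% figure carries over to reduced doses, the same named step would give a child on the tablet materially less exposure than a child on the powder. The protocol does not say whether that is intended.

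**Working it through.** **Inputs (mg; full dose / reduction 1 / reduction 2).** Powder, Table 3: 600 / 400 / 300 at 10 to < 20 kg; 900 / 600 / 400 at 20 to < 40 kg. Dispersible tablet, Table 4: 800 / 500 / 300 and 1200 / 900 / 300. The 500 mg tablet ladder (Table 3 and Table 4 at ≥ 40 kg, and Table 5): 1500 / 1000 / 500. Exposure ratio, powder to tablet at the same milligram dose: about 1.35 (Section 1.6.1).

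**Reproducing the plan's full doses.** Powder dose × 1.35: 600 × 1.35 = 810 (printed 800); 900 × 1.35 = 1215 (printed 1200). Both agree after rounding to 100 mg.

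**The same check at every step.** Relative exposure = tablet mg ÷ (powder mg × 1.35), assuming dose proportionality.

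| Band | Step | Powder | Tablet | Tablet ÷ powder | Powder × 1.35 | Relative exposure |
|---|---|---|---|---|---|---|
| 10 to < 20 kg | Full | 600 | 800 | 1.33 | 810 | 0.99 |
| 10 to < 20 kg | 1 | 400 | 500 | 1.25 | 540 | 0.93 |
| 10 to < 20 kg | 2 | 300 | 300 | 1.00 | 405 | 0.74 |
| 20 to < 40 kg | Full | 900 | 1200 | 1.33 | 1215 | 0.99 |
| 20 to < 40 kg | 1 | 600 | 900 | 1.50 | 810 | 1.11 |
| 20 to < 40 kg | 2 | 400 | 300 | 0.75 | 540 | 0.56 |

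The column of powder × 1.35 is a consistency check and not a set of proposed doses.

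**Sensitivity to the word approximately.** Taking an assumed ratio of 1.25 to 1.45, relative exposure at step 2 is 300/375 = 0.80 to 300/435 = 0.69 in the lower band, and 300/500 = 0.60 to 300/580 = 0.52 in the upper band. For the printed step 2 doses to match the powder, the ratio would have to be 1.00 and 0.75.

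**A check that does not use the 35% figure.**

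| Ladder | Step 2 as share of full dose | Cut from step 1 to step 2 |
|---|---|---|
| Powder, 10 to < 20 kg | 300/600 = 50% | 1 − 300/400 = 25% |
| Powder, 20 to < 40 kg | 400/900 = 44% | 1 − 400/600 = 33% |
| 500 mg tablets | 500/1500 = 33% | 1 − 500/1000 = 50% |
| Dispersible, 10 to < 20 kg | 300/800 = 37.5% | 1 − 300/500 = 40% |
| Dispersible, 20 to < 40 kg | 300/1200 = 25% | 1 − 300/900 = 67% |

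The upper-band dispersible entry lies outside the range of the other ladders on both measures. The lower-band entry lies inside it, so the case against that entry rests on the 35% rationale alone.

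**Possible innocent explanations.** Tablet strength: 100 mg and 300 mg tablets make any multiple of 100 mg, and Table 4 itself prints 500 mg. Rounding: rounding to the nearest 100 mg moves a dose by at most 50 mg, while the gaps are 405 − 300 = 105 mg and 540 − 300 = 240 mg. Stated intent: neither Section 5.1.2 nor Table 6 sets a separate exposure target for reduced tablet doses.

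**The case against.** The strongest reply is that Section 1.6.1 matches exposure only at the full dose. The 35% sentence points to Tables 1 and 2, and nothing in Section 5.1.2 promises that reduced doses are matched across dosage forms. This stands, and it is why the finding is an unexplained inconsistency and not a broken rule. It does not remove the question, because the reason given is a property of the dosage form and the text does not confine it to full doses.

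The step 1 ratios (1.25 and 1.50) fall on either side of 1.35, so Table 4 may never have been built by converting Table 3. That is possible. The step 1 differences (500 against 540 mg, 900 against 810 mg) are minor and are not counted here. But this scatter does not explain why the upper-band tablet dose then falls below the powder dose, or why it drops by two-thirds in one step.

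The comparison between ladders is thin: there are only three distinct comparators, and their cuts already range from 25% to 50%. It therefore supports singling out the 20 to < 40 kg entry only.

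The practical reach is small, and this also stands. A participant would have to be under 12 years, under 40 kg, on active drug, on a contingency form, and in need of two successive reductions, which are reversible. Neither document shows that the dispersible tablet was used. SAP Section 2 records that dosing was paused as of 1 May 2024 and that the study was later terminated. The Pharmacy Manual, which might hold an explanation, is a separate document that was not available for this review.

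**Conclusion.** The concern holds. Against the protocol's own 1.35 ratio, the two step 2 tablet entries correspond to about 0.74 (10 to < 20 kg) and 0.56 (20 to < 40 kg) of the matching powder exposure, compared with 0.99 at full dose. The milligram comparison is certain. The exposure figures are conditional: they assume dose proportionality and that an approximate single-dose ratio from healthy volunteers applies to children on daily dosing. The evidence is stronger for the 20 to < 40 kg entry, which is anomalous even without that ratio. Whether the sponsor intended the difference is unknown, so confidence is medium. It should be resolved because these are printed doses for children with adverse events. It has no bearing on power or on the primary analysis.

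**What to change.** The sponsor should reconcile the two step 2 dispersible-tablet entries of Table 4 with Table 3 and Section 1.6.1, or add a statement that the 35% adjustment is not meant to apply to reduced doses, with the reason. This review takes no view on which entry is right.

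Optionally, the study report could state whether any participant received a step 2 dispersible-tablet dose. SAP Section 8.3.1 already summarizes dose reductions, though not by dosage form or reduction step, and Section 5.1.2 requires every dose modification to be recorded on the eCRF.

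The cost is low: one clarifying note or table correction and, if wanted, one count from dose-modification records already collected. No extra participants or procedures are needed.
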